7.4 Sample Banking

As agreed by the subject on the signed informed consent form (ICF), his or her blood (and blood products) will be kept in the Sponsor's lab or designated facility equipped with freezers (at -80 °C) and may be used by the sponsor for research. The ICF will include the subject's right to release or restrict their sample for purpose of research by the sponsor.

Each sample will be identified by a unique number on a bar-coded label (sample ID) which will not have any personal information in order to maintain subject confidentiality. Only the study site staff will keep a matching list of sample barcode numbers, subject identifiers, subject names, and visit dates to fully identify these samples.

Clinical Study Protocol	
Title: Plasma-Based Next-Generation Sequencing for Pathogen Detection and Quantification in Children with Musculoskeletal Infections	
Supersedes: 0.8	Document Number: KDG-002 Clinicaltrials.gov #: NCT03846804
	Effective Date: 19Oct2021

Page: 17 of 30

8 SAFETY MONITORING AND REPORTING

No unexpected adverse events or side effects related to the conduct of the protocol are anticipated. All venous samples will be collected by routine techniques performed by qualified phlebotomists and/or licensed health care personnel. All adverse events will be reported to the IRB and to the Medical Monitor.

Medical Monitor: [name] , M.D., [contact]; [contact].

9 CLINICAL ADJUDICATION

9.2 Adjudication Process

NA

9.3 Data Review

Upon the study completion, the comparison between Karius NGS testing and standard culture methods for pathogen identification will be reviewed by [name] and Karius. The study results will be summarized in a peer-reviewed publication.

10 STATISTICAL CONSIDERATIONS

10.1 General Conditions for Statistical Analysis

Positive and negative agreement (percentage) will be used to compare culture and NGS for pathogen identification. Correlation between inflammatory markers and cfDNA quantification will be compared using Spearman's coefficient. Lastly, simple regression modeling will be used to assess the ability of cfDNA to predict severe disease.

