Study Objectives:	
 1. To evaluate and compare pathogen identification of children with musculoskeletal infections (MSKI) using Karius® plasma-based quantitative Next-Generation Sequencing Test (Karius Test) and standard culture methods. 2. To examine the kinetics of pathogen cell-free DNA (cfDNA) in the plasma of children with MSKI and compare the quantity of cfDNA to clinical symptoms and inflammatory markers, C-reactive protein (CRP), Erythrocyte sedimentation rate (ESR), and procalcitonin (PCT), a biomarker thought to be more specific for bacterial infections. 3. To evaluate whether samples quantitative cfDNA predicts severe disease in children with MSKI.
Study Design:	We will prospectively enroll children evaluated at Riley Hospital for Children (RHC) with musculoskeletal infections (osteomyelitis, septic arthritis, or pyomyositis) over a 12-24-month period. Eligible subjects will be identified by referral from the infectious diseases and orthopedic services at RHC. Subjects and their parent(s) or guardian(s) will be informed of the study and, upon providing informed consent, will be enrolled in the study. Study samples will be collected at time points that closely parallel clinical testing as performed during routine, standard care for treatment of MSKI. Immediately after enrollment, up to two detection blood samples will be obtained for real-time NGS testing at Karius Laboratory (Redwood City, CA) to determine if additional study samples will be obtained. Detection of a pathogen by NGS will be interpreted as a positive result that qualifies the collection of subsequent study samples. Pathogen identification by NGS will be compared to standard cultures methods, and quantitative cfDNA will be evaluated over time.
Duration of Study:	12-Month Period
Number of Sites:	1: Riley Hospital for Children
Sample Size:	38 Subjects

	Clinical Study Protocol
Title: Plasma-Based Next-Generation Sequencing for Pathogen Detection and Quantification in Children with Musculoskeletal Infections	
Supersedes: 0.8	Document Number: KDG-002 Clinicaltrials.gov #: NCT03846804
	Effective Date: 19Oct2021

Page: 9 of 30

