1.2 Rationale for the Study

A culture-independent molecular test, such as the Karius® plasma-based next-generation sequencing (Karius Test) test, would not be prone to the aforementioned barriers and has the potential to increase pathogen detection allowing for targeted antimicrobial therapy.

Additionally, quantitative NSG has the potential to improve another component of the complex management of children with MSKI—length of therapy (LOT). Typically, length of therapy for MSKI in children is 2-6 weeks depending on the infection type and severity, however, variability in this practice exists [5,6]. Ultimately LOT is typically determined by clinical symptoms and inflammatory makers (e.g., C-reactive protein (CRP) and erythrocyte sedimentation rate (ESR)) at the end of the pre-determined timeframe. This approach, while often effective, is challenging in children given that the clinical exam can be unreliable and inflammatory markers are non-specific, often influenced by intercurrent illnesses or recent procedures. An objective assay with improved specificity, such as the Karius Test, which has the ability to quantitate cell-free pathogen DNA (cfDNA) and has been shown to correlate with clinical findings in other disease states [7], could allow for a tailored treatment approach and address an unmet need for children with MSKI.

Finally, the ability of the Karius Test to quantitate cfDNA has the potential to inform disease severity and potentially predict complications in children with MSKI. While numerous proposed strategies have been published to develop a prediction algorithm for disease severity in children with MSKI, each of these methods has significant limitations [8], and none involve quantification of cfDNA. If the Karius Test could be used to predict severe disease, it could have a significant impact on early management of this complex disease.

	Clinical Study Protocol	
	Title: Plasma-Based Next-Generation Sequencing for Pathogen Detection and Quantification in Children with Musculoskeletal Infections	
Supersedes: 0.8	Document Number: KDG-002 Clinicaltrials.gov #: NCT03846804	
	Effective Date: 19Oct2021	Page: 10 of 30

Taken together, the Karius Test has the potential to significantly impact antibiotic utilization and quality of care for children with MSKI. In this proposal, we seek to investigate the utility of this novel technology in children with MSKI.

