2 STUDY OBJECTIVES AND ENDPOINTS

2.1 PRIMARY OBJECTIVES

- 1) To evaluate and compare pathogen identification of children with musculoskeletal infections using Karius plasma-based quantitative NGS test (Karius Test) and standard culture methods. We hypothesize that the Karius Test will have a high positive agreement for culture positive samples and increase pathogen detection in culture-negative infections.
- 2) To examine the kinetics of pathogen cell-free DNA (cfDNA) in the plasma of children with MSKI and compare the quantity of cfDNA to clinical symptoms and inflammatory markers, CRP, ESR, and procalcitonin (PCT), a biomarker thought to be more specific for bacterial infections. We hypothesize that the cfDNA quantity will correlate strongly with clinical symptoms as well as inflammatory markers (CRP, ESR and PCT).
- 3) To evaluate whether initial detection samples quantitative cfDNA predicts severe disease¹ in children with MSKI. We hypothesize that cfDNA quantity at admission will correlate with severe or complicated MSKI.

¹Severe disease defined by any of the following: need for intensive care unit (ICU) care, infection in two or more non-contiguous anatomic sites (disseminated disease), complicated disease (need for more than 1 debridement procedure, deep vein thrombosis [DVT] or thromboembolic disease, pathologic fracture)

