2.3 PRIMARY ENDPOINT MEASURES

- 1) To evaluate and compare pathogen identification of children with musculoskeletal infections using Karius Test NGS and standard culture methods:
 - a. Describe pathogen identification by Karius Test vs. standard culture methods
- 2) To examine the kinetics of pathogen cell-free DNA (cfDNA) in the plasma of children with MSKI and compare the quantity of cfDNA to clinical symptoms and inflammatory markers, CRP, ESR, and procalcitonin (PCT), a biomarker thought to be more specific for bacterial infections.

	Clinical Study Protocol
Title: Plasma-Based Next-Generation Sequencing for Pathogen Detection and Quantification in Children with Musculoskeletal Infections	
Supersedes: 0.8	Document Number: KDG-002 Clinicaltrials.gov #: NCT03846804
	Effective Date: 19Oct2021 Page: 11 of 30

- a. Determine quantification of cf DNA in molecules per microliter (MPM) at each time point using the Karius Test.
- b. Determine CRP, ESR, PCT at each timepoint and compare to cfDNA MPM.

3) To evaluate whether initial detection sample quantitative cfDNA predicts severe disease in children with MSKI.

- a. Determine the correlation of cfDNA level in MPM to severity of infection (defined in SECTION 2.1)

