3 STUDY DESIGN

This is a prospective study of children 6 months to 18 years of age (inclusive) with the diagnosis of MSKI at Riley Hospital for Children (Indianapolis, IN) over a 12-month period. Eligible subjects will be identified by referral from the infectious diseases and orthopedic services at RHC. Subjects will be identified and screened for eligibility (Section 5.3) by the study team. Subjects and their parent(s) or guardian(s) will be informed of the study and, upon providing informed consent, will be enrolled in the study.

Study samples will be collected to coincide with routine clinical care. Samples will be collected when sufficient sample is available after routine care samples are obtained. Additional venipunctures specific for collection of study samples will be performed only with participant's consent.

Collection of NGS samples for real-time testing:

Detection samples will be collected prior to any surgical procedures and will be sent to Karius® Laboratory (Redwood City, CA) for real-time testing to determine if the pathogen is detected by NGS. Karius will notify the study team of the result(s). A positive result for any detection sample will qualify the collection of subsequent study samples. Detection samples will be collected within 96 hours of enrollment, and if applicable, 12-72 hours after the first sample, upon any re-admission for MSKI, or when prior detection sample results are inconclusive.

Collection of subsequent study samples

If NGS testing identifies a pathogen in the detection sample(s), subsequent study samples will, will be collected \geq 48 hours after previous sample collected. When the Detection NGS result(s)

Clinical Study Protocol	
Title: Plasma-Based Next-Generation Sequencing for Pathogen Detection and Quantification in Children with Musculoskeletal Infections	
Supersedes: 0.8	Document Number: KDG-002 Clinicaltrials.gov #: NCT03846804
	Effective Date: 19Oct2021
	Page: 12 of 30

is inconclusive or still pending, study samples may be collected at the appropriate timepoint(s). Collected sample(s) will be sent to Karius with qualifying result(s) from the Detection NGS sample(s). Up to 4 samples, including detection samples, will be collected per inpatient admission. (**Figure 1**)

[figure not shown]

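### The plan says initial-sample cfDNA predicts severe disease, but severity has no time condition and is largely missing from the listed data fields, so the planned regression supports association only

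*Combined protocol and SAP*

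**What the plan says.** Four places use the language of prediction:

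- Synopsis, objective 3: "To evaluate whether samples quantitative cfDNA predicts severe disease in children with MSKI" (the initial sample is not named here).
- Section 2.1, objective 3: "To evaluate whether initial detection samples quantitative cfDNA predicts severe disease".
- Section 2.3, heading of endpoint 3: "To evaluate whether initial detection sample quantitative cfDNA predicts severe disease in children with MSKI".
- Section 10.1: "simple regression modeling will be used to assess the ability of cfDNA to predict severe disease". No model form, time origin, outcome window or at-risk set is given.

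Two places use the language of association. The hypothesis under objective 3 in section 2.1 expects cfDNA at admission to correlate with severe or complicated infection. The only measure listed under endpoint 3 is "Determine the correlation of cfDNA level in MPM to severity of infection".

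Section 2.1 counts a child as severe if any one of five things applies: ICU need, infection at two or more non-contiguous sites, more than one debridement, DVT or other thromboembolic disease, or pathologic fracture. It says nothing about when these must begin.

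On sampling, section 3 states "Detection samples will be collected prior to any surgical procedures", and section 5.4 excludes children operated on before the NGS sample. Section 3 also allows the detection sample up to 96 hours from enrollment.

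**The concern.** To say that a marker predicts an outcome, the marker must be measured before the outcome occurs. If a child already in intensive care, or already known to have several infected sites, counts as an event, a raised cfDNA level in that child shows how ill the child is now. It does not show what will happen next. Pooled with children who deteriorate later, such cases could carry the whole result.

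This matters because section 1.2 attaches a clinical use to the forward-looking claim: "If the Karius Test could be used to predict severe disease, it could have a significant impact on early management of this complex disease". Section 9.3 plans a peer-reviewed publication. A reader of that paper would take a positive regression labeled as prediction to mean that the test identifies children before they become severe. Followed as written, the plan gives no way to show that.

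**Working it through.** **1. The plan's own figure.** Section 10.4 gives 50 expected admissions and participation above 75%: 50 × 0.75 = 37.5, rounded up to 38. This reproduces the target. It is a feasibility figure. No severity rate, effect size, alpha or power is stated.

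**2. Each severity component against sampling time and the listed fields** (section 10.2 and Appendix C).

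| Component | Must it follow the first sample? | Listed field |
|---|---|---|
| ICU need | No | None |
| Two or more non-contiguous sites | No | Infection location: one name field, undated |
| More than one debridement | Yes, because surgery before sampling is excluded | Surgery yes/no: no count, no date |
| DVT or thromboembolism | No | None |
| Pathologic fracture | No | None |

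The exclusions in section 5.4 do not remove children who are already severe. Section 10.2 lists the NGS sample time, but the Appendix C form gives NGS results by sample label without a time. Section 9 marks adjudication as not applicable. The case report form paragraph in section 11.3 names further content, none of it a severity item. From the listed fields, therefore, the composite can be neither built in full nor placed before or after the sample.

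**3. Illustration of size (all inputs assumed).** Take 38 children with 20%, 30% or 40% severe: 7.6, 11.4 and 15.2, rounded to 8, 11 and 15. Log cfDNA is normal with SD 1. Children already severe are shifted by √2 × Φ⁻¹(0.75) = 1.414 × 0.6745 = 0.954, which gives AUC 0.75. Later cases have no shift (AUC 0.50). The analysis is a one-predictor logistic model, counted as positive if the likelihood-ratio p is below 0.05 and the slope is above zero (nominal 2.5%). There were 4,000 runs per cell; the Monte Carlo error is at most about √(0.3 × 0.7 / 4000) = 0.007 at a rate of 30%.

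| Share already severe | Cases already severe / all severe | Composite positive |
|---|---|---|
| About a quarter | 2/8, 3/11, 4/15 | 0.097, 0.104, 0.104 |
| About half | 4/8, 6/11, 8/15 | 0.223, 0.281, 0.317 |
| About three quarters | 6/8, 8/11, 11/15 | 0.430, 0.483, 0.529 |

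The later-only analysis is positive in 0.025–0.035 of runs throughout. At about half, the expected composite AUC is (4 × 0.75 + 4 × 0.50)/8 = 0.625, (6 × 0.75 + 5 × 0.50)/11 = 0.636 and (8 × 0.75 + 7 × 0.50)/15 = 0.633, and the median odds ratio is about 1.7 per SD. If later cases also have AUC 0.75, the composite AUC is 0.75 and the label does no harm.

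**4. Precision of a later-only estimate.** With half already severe, the later events and non-severe children number 4 vs 30, 5 vs 27 and 7 vs 23. Hanley–McNeil variance: [A(1−A) + (m−1)(P₁−A²) + (n−1)(P₂−A²)]/(mn), with P₁ = A/(2−A) and P₂ = 2A²/(1+A).

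- A = 0.70, m = 4, n = 30: (0.21 + 3 × 0.0485 + 29 × 0.0865)/120 = 0.0239; SE 0.154; half-width 1.96 × 0.154 = 0.30.
- A = 0.70, m = 7, n = 23: (0.21 + 6 × 0.0485 + 22 × 0.0865)/161 = 0.0149; SE 0.122; half-width 0.24.
- A = 0.50: intervals of about 0.19–0.81 (4 events) to 0.25–0.75 (7 events).

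For the composite at A = 0.70, the half-widths are 0.22, 0.20 and 0.18 with 8, 11 and 15 events.

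**The case against.** **The plan partly means association.** The hypothesis and endpoint 3a speak of correlation, and section 1.2 gives informing disease severity as one aim. This stands. The association would be genuine, and the simulated percentages are not false-positive rates for endpoint 3a. But the same regression is called prediction in four places, so the wording has to be settled.

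**The pooled regression cannot be run from the listed fields.** Correct. Staff would need the medical record to build the outcome, and the same record could give the order of events. This makes the lack of severity fields the firmer defect and the lack of dates the second. It would be too strong to say that order is unrecoverable: section 10.2 keeps a log linking subjects to medical records. But no readable passage plans a chart review for severity; section 10.6 plans record review for demographics only.

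**The data set is headed as minimal, and the form shown is not the whole CRF.** Fair. Section 11.3 names items absent from Appendix C, and the content of the schedule of events is not in the text available. Nothing is inferred from that gap.

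**No sentence says that severity present at sampling counts.** Also true. A reader might take this as a stated rule. It follows only from a definition with no time limit and exclusions that leave such children in.

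**A later-only analysis is too small to help.** With 4 to 7 events it cannot separate an AUC of 0.50 from 0.75. It is worth reporting only as a description.

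**Conclusion.** The concern holds in this form: the plan does not define or list its severity outcome in a way that can support a conclusion of prediction. That rests on the text alone and is firm. A regression on the composite supports an association between initial-sample cfDNA and severity.

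The size is not known. The severe rate, the share already severe and both AUCs are assumed, and the model gives every child a quantified value although section 3 allows for samples in which no pathogen is found. Under those assumptions, apparent prediction with no later signal appears in about 10% to 53% of trials, depending mainly on the share already severe, against about 3% for later events only. If the later signal is as strong as the early one, no harm follows.

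A reader might infer that a positive result would be spurious. The documents do not support that: the association could be real, and only the word predicts would lack support. The point should be corrected, but it does not invalidate the study.

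**What to change.** 1. Add the five severity components to section 10.2 and the CRF, each with the date and time first recognized, and add the NGS sample date and time to the CRF.
2. In the synopsis, sections 2.1 and 2.3 and section 10.1, describe the primary analysis as the association of initial-sample cfDNA with the severity composite, reported as an estimate with 95% CI.
3. Tabulate each component as recognized before or after the sample. As a descriptive secondary estimate with 95% CI, report the association limited to severity first recognized after the sample in children not already severe. Keep predictive wording for that estimate, and state that a non-significant result will not be read as no prediction.

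The cost is six CRF items (five dated severity items and the sample time), chart review for 38 children through the existing link log, and wording in four places. No extra blood or patients are needed, and the target stays at 38. Two limits remain. The later-only estimate is imprecise (half-width about 0.24–0.30 at AUC 0.70 with 7 to 4 later events). Recognition can also lag onset, so some events dated after the sample may already have been present.

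Separately, the synopsis says "Immediately after enrollment, up to two detection blood samples will be obtained for real-time NGS testing" while section 3 allows up to 96 hours from enrollment. The two statements must be reconciled.

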10.2 Analysis Data Sets

MINIMAL CLINICAL DATA SET

** All of these data will be striped of protected health information (PHI). The Investigator will maintain a log that can link these subject ID and sample IDs to medical record numbers and sample-collection dates.

Variable	Acronym definition	Type of data
Subject ID	Subject Identifier	Numerical
Sample ID	Sample Identifier (i.e., IP1)	Numerical

	Clinical Study Protocol	
	Title: Plasma-Based Next-Generation Sequencing for Pathogen Detection and Quantification in Children with Musculoskeletal Infections	
Supersedes: 0.8	Document Number: KDG-002 Clinicaltrials.gov #: NCT03846804	
	Effective Date: 19Oct2021	Page: 18 of 30

Admission Time	Date and time of hospital admission	Date and time
Discharge Time	Date and time of hospital discharge	Date and time
Sample Time	Date and time of NGS sample collection	Date and time
Age	Age at the time of diagnosis of MSKI	Years
Sex		F/M
Race		Nominal
Infection Type	Acute hematogenous osteomyelitis (AHO), Septic Arthritis, Pyomyositis	Nominal
Infection Location	Name of bone/joint infected	Nominal
Days of Symptoms	Days of symptoms (number) related to MSKI (fever, pain) prior to hospital admission	Numerical
Antibiotic Prior Admit	Antibiotic given prior to admission (Y/N)	Yes/No
Antibiotic Name	Name of initial antibiotic(s) given for MSKI	Nominal
Antibiotic Time	Date and time initial antibiotic(s) given	Date and time
Surgical Procedure	Was a surgical procedure performed	Yes/No
Culture Pathogen ID	Name of pathogen by culture	Nominal
Culture source	Source of culture (i.e., blood, bone, synovial fluid)	Nominal
NGS Pathogen ID	Name of pathogen by NGS	Nominal
NGS Quantification	Molecule per microliter (MPM) of cfDNA	Numerical
WBC	White blood cell count	Numerical
WBC Timepoint	Time and Date of WBC collection	Date and time
CRP	C-reactive protein	Numerical
CRP Timepoint	Time and Date of CRP collection	Date and time

	Clinical Study Protocol
	Title: Plasma-Based Next-Generation Sequencing for Pathogen Detection and Quantification in Children with Musculoskeletal Infections
Supersedes: 0.8	Document Number: KDG-002 Clinicaltrials.gov #: NCT03846804
	Effective Date: 19Oct2021

ESR	Erythrocyte sedimentation rate	Numerical
ESR Timepoint	Time and Date of ESR collection	Date and time
PCT	Procalcitonin	Numerical
PCT Timepoint	Time and Date of PCT collection	Date and time

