10.7 Analysis

Statistical analysis is outlined in [Section 10.1](#)

	Clinical Study Protocol	
	Title: Plasma-Based Next-Generation Sequencing for Pathogen Detection and Quantification in Children with Musculoskeletal Infections	
Supersedes: 0.8	Document Number: KDG-002 Clinicaltrials.gov #: NCT03846804	
	Effective Date: 19Oct2021	Page: 20 of 30

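### Objective 3 is worded as prediction, but the plan names no measure of discrimination, no model type and no scale for cfDNA beyond MPM

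*Combined protocol and SAP*

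**What the plan says.** Section 2.1 lists three primary objectives. The third is "To evaluate whether initial detection samples quantitative cfDNA predicts severe disease", with the hypothesis "We hypothesize that cfDNA quantity at admission will correlate with severe or complicated MSKI". Its footnote defines severe disease as any one of ICU care, infection at two or more non-contiguous sites, or "complicated disease (need for more than 1 debridement procedure, deep vein thrombosis [DVT] or thromboembolic disease, pathologic fracture". The outcome is therefore yes or no.

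The analysis in section 10.1 is "simple regression modeling will be used to assess the ability of cfDNA to predict severe disease". Section 10.7 adds nothing and refers back to 10.1. Endpoint 3a in section 2.3 reads "Determine the correlation of cfDNA level in MPM to severity of infection". The data set in section 10.2 lists the predictor as "Molecule per microliter (MPM) of cfDNA". Section 10.1 uses CRP, ESR and PCT only for Spearman correlation with cfDNA. On early prediction of severe disease, section 1.2 says that "it could have a significant impact on early management of this complex disease".

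**The concern.** One primary aim is described as prediction, as correlation and as regression, and none of the three descriptions names the quantity to be reported. A slope with a p-value shows association. It does not show how well cfDNA separates children who will have severe disease from those who will not, and section 1.2 rests the test's possible clinical value on that separation.

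Several choices that can change the result are also left until the data are seen: the type of model, the scale of cfDNA, the value given to children with nothing detected, and which of up to two detection samples supplies the predictor. Scale matters because one or two very large counts can dominate a fit on untransformed MPM. Objective 2 is protected because Spearman's coefficient uses ranks. The regression for objective 3 has no such protection.

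**Working it through.** **Sample size.** Section 10.4 gives at least 50 admissions and more than 75% participation: 50 × 0.75 = 37.5, rounded up to 38. The figure reproduces, but it is a feasibility count. It uses no alpha, power or effect size, so objective 3 has no stated power to check.

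**Inputs that the documents do not give, assumed here.**
- Severe disease in 20%, 30% or 40% of 38 children, which is 8, 11 or 15 events.
- True AUC 0.75.
- Two-sided alpha 0.05.
- MPM log-normal, with within-group SD 0.5 or 1.0 on the log10 scale.

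**Precision of an AUC.** The Hanley-McNeil formula, with m severe and k non-severe children, is

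SE² = [A(1−A) + (m−1)(Q1−A²) + (k−1)(Q2−A²)] / (mk), with Q1 = A/(2−A) and Q2 = 2A²/(1+A).

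For A = 0.75: Q1 = 0.600, Q2 = 0.643, A² = 0.5625. With m = 11 and k = 27, SE² = (0.1875 + 10 × 0.0375 + 26 × 0.0804)/297 = 0.00893, so SE = 0.094.

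| Severe / not severe | SE | 95% CI for an AUC of 0.75 |
|---|---|---|
| 8 / 30 | 0.108 | 0.54 to 0.96 |
| 11 / 27 | 0.094 | 0.56 to 0.94 |
| 15 / 23 | 0.085 | 0.58 to 0.92 |

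**Effect of scale on power.** Simulation with 1,000 trials per cell, n = 38, group separation √2 × z(0.75) = 0.954 SD, and logistic regression with one predictor:

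| log10 SD | Events | LR test, raw / log | Loss (points) | Wald test, raw / log | Loss (points) |
|---|---|---|---|---|---|
| 0.5 | 8 | 55.5 / 67.0% | 11.5 | 37.0 / 59.9% | 22.9 |
| 0.5 | 11 | 65.3 / 75.9% | 10.6 | 46.2 / 69.8% | 23.6 |
| 0.5 | 15 | 70.7 / 81.7% | 11.0 | 46.9 / 76.8% | 29.9 |
| 1.0 | 8 | 47.2 / 68.4% | 21.2 | 16.1 / 60.0% | 43.9 |
| 1.0 | 11 | 54.6 / 75.2% | 20.6 | 18.0 / 68.7% | 50.7 |
| 1.0 | 15 | 62.1 / 85.2% | 23.1 | 16.7 / 80.0% | 63.3 |

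The loss is about 11 to 23 points by likelihood ratio (LR). The plan names no test, so the Wald columns show only how far the choice of test matters. When there is no true association, the raw-scale LR test rejects about 7.5 to 8.5% of the time (log scale 5.4 to 8.1%), so its raw-scale power is slightly flattered. If only 25 children had a usable value (5 to 10 events), the LR loss would be about 5 to 14 points.

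A second set-up assumed 25% severe, AUC 0.76, the lowest quarter of non-severe values undetected, and log10 SD 0.7 / 1.0 / 1.3. LR power was 61/55/54% on raw MPM and 75/74/74% on log10 MPM, a loss of 14/19/20 points. In a repeat with 1,000 trials per SD, raw MPM gave 61/54/53% and Firth-penalised regression on log10 MPM about 72/70/71%, a gain of 11/16/18 points.

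**What a CRP comparison could show.** For two markers measured in the same children, the SE of the AUC difference is √[2 SE²(1−r)]. With both AUCs near 0.75 and r assumed 0.3 to 0.5, the 95% half-width across 8 to 15 events is 1.96 × that SE, about 0.17 to 0.25. The difference detectable with 80% power is 2.802 × that SE, about 0.24 to 0.36.

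**The case against.** Four stronger readings are tempting, and the documents support none of them.

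- A reader might infer that the plan commits to untransformed MPM. It does not. MPM is the only unit named, but section 10.1 states no scale, and a unit does not rule out a log transform. The fault is that the raw scale is left open.
- A reader might take it as known that MPM is highly skewed. The documents give no distribution, range or detection limit. The simulated data were generated log-normal, which favours the log-scale model by construction.
- A reader might conclude that regression cannot measure prediction. Logistic regression gives predicted risks and an AUC directly. With one predictor, the AUC is the same on the raw or the log scale because it depends only on ranks. Scale affects the slope, the test and the predicted risks, not discrimination.
- A reader might say that the study must show cfDNA to be better than CRP. No objective, endpoint or hypothesis claims this, and n=38 could show only very large differences.

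What still stands is that a primary objective worded as prediction has no prespecified measure of predictive performance, and that the choices left open can change the result.

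**Conclusion.** The point holds as a gap in specification with a cheap and better alternative. It is not a demonstrated error of scale. That no discrimination measure is planned follows from the text alone and needs no assumption. The interval widths rest on an assumed 8 to 15 events and an AUC of 0.75. The power loss of about 11 to 23 points rests further on log-normal MPM, the assumed spread, the use of raw MPM and the LR test. It illustrates what the open wording permits and does not forecast this study's result.

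A related gap bears on the same objective. The data set in section 10.2 and the form in Appendix C list no field for ICU care, DVT or thromboembolism, pathologic fracture or number of debridements. Surgery is recorded only as yes or no, and infection site only as the name of the bone or joint. The outcome to be predicted lacks a listed source for most of its components. The change should be made before the analysis is run.

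**What to change.** Replace the clause in section 10.1 with:

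> Severe disease (yes/no) will be analysed by Firth-penalised logistic regression on log10 MPM of the first detection sample. All children will be included; non-detections will be set to one fixed value below the lowest reportable MPM, chosen before analysis. Predictive ability will be reported as the AUC with 95% CI. The AUC of the CRP nearest the same draw will be reported in the same children as a descriptive comparison only; the sample size cannot establish superiority of either marker.

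Penalisation is proposed because events will be few. The documents give no lowest reportable MPM, so the laboratory must supply it. Section 2.3(3a) should be reworded to match. A further model adjusting for *S. aureus* against other organisms is not advised: it adds a covariate with few events and is undefined for children in whom no organism is found.

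Add ICU care, number of debridements, DVT or thromboembolism, pathologic fracture and dissemination to section 10.2 and Appendix C, taken from the medical record.

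The cost is a few sentences, a few lines of code and a few extra chart-review fields, with no new samples. The downside is that a wide AUC interval will be shown openly.
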